#### 3.4 Examination of Patient Subsets

Emerging data have identified patients with baseline blood lactate levels ≤ 2.0 mM at rest during the submaximal exercise test and patients with baseline resting heart rate ≤80 bpm during the submaximal exercise test as particular subgroups of interest. Analyses of submaximal exercise testing parameters data may be performed on these subgroups of interest.

#### 3.5 Multiple Comparisons

No adjustments for multiplicity will be considered for analysis of Part 1 data.

## 3.6 Missing Data

Missing data will not be imputed for the primary analysis of safety, PK, PD, or exploratory efficacy endpoints. The planned statistical methods use all available data, therefore no imputation is planned for the primary analysis of the primary and secondary efficacy endpoints (i.e., peak work and 6MWD). Sensitivity analyses may be performed as appropriate to assess the impact of missing data.

#### 3.7 Visit Windows

### 3.7.1 **Definition of Study Day**

Study day is the day relative to the first dose of study drug administration. Study day for events on or after the date of the first dose will be defined as the number of days from the date of the first dose of study drug, plus 1 day, so that the date of the first dose will be defined as Day 1.

For events before the date of the first dose, study day will be calculated as the difference in days between the date of the first dose and the date of interest. Thus, the day before the date of the first dose will be defined as Day -1.

#### 3.7.2 **Definition of Study Baseline**

The average of Screening and Day 1 assessments will be used as baseline for 6MWT. For all other parameters, study baseline is defined as the last non-missing observation obtained prior to administration of the first dose on Study Day 1. Baseline will be defined as analysis visit 0.

#### 3.7.3 Analysis Visits

The CRF nominal study visits will be used for all safety analyses. For efficacy analyses or when otherwise specified, summaries by visit will be done using analysis visits defined below.

Analysis Visit Number	Label	Protocol Visit Number	Target Study Day
0	Baseline	1, 2	≤1
4	Week 4	5, 6	28
8	Week 8	8	56
12	Week 12	10.11	84

#### 3.7.4 Analysis Windows for Unscheduled Visits

Unscheduled visits will be reflected in summarization of changes to worst post-baseline measures.

Additionally, unscheduled assessments will be used in the place of missing scheduled efficacy and safety assessments, if the unscheduled assessment was collected within ±7 days of the scheduled assessment. Study day will be calculated for each unscheduled assessment and compared to the protocol defined study day for each visit. In general, analysis windows for unscheduled visits will be defined as follows:

Analysis Visit	Target Study Day	Analysis Window
0	1	Study Day ≤1
1 (Safety Only)	7	$2 \le$ Study Day $\le 10$
2 (Safety Only)	14	$11 \le $ Study Day $\le 20$
4	28	21 ≤ Study Day ≤ 35
8	56	49 ≤ Study Day ≤ 63
12	84	$77 \le \text{Study Day} \le 91$

Records from unscheduled visits that do not fall within an analysis window will be listed, but will not be analyzed.

## 3.7.5 Selection of Data in the Event of Multiple Records in a Visit

If multiple assessments fall within the same analysis visit, the assessment closest to the target visit day specified in the protocol study procedures will be used. If two assessments are equidistant from a post-baseline target visit day, the earlier assessment will be used.

## 3.8 Rounding

The method of rounding for data presentation is provided in Appendix 2.

#### 4. STUDY POPULATION

## 4.1 Disposition of Patients

Enrollment and disposition will be summarized. A patient will be defined as enrolled if they sign the informed consent form. A disposition summary will include the number and percentage of patients who:

- Enrolled in the study
- Are in the safety analysis set
- Are in the full analysis set
- Number of patients dose escalated (Cohort 1 only)
- Completed treatment through Week 12
- Prematurely discontinued from study treatment
- Completed the study
- Prematurely terminated from the study.

The disposition summary will also include the primary reason for discontinuation from study treatment or termination from the study.

Disposition summaries will be presented by randomized treatment. Percentages will be based on the number of randomized patients.

A listing of patient disposition will include the date of first dose of study drug, date of last dose of study drug, total weeks of treatment, study treatment completion status, study completion status, and reason(s) for study drug discontinuation and/or study termination.

#### 4.2 Protocol Deviations

Where available, protocol deviations will be listed by deviation category (e.g., eligibility criteria, out of window visit, serious adverse event (SAE) reporting, study procedures, treatment procedures). All deviations, including major protocol deviations that could potentially affect the efficacy or safety conclusions of the study, will be identified prior to database lock. Protocol deviations will be listed in a data listing and summarized by deviation category.

## 4.3 Demographics and Baseline Characteristics

Demographic and baseline characteristics summaries, for patients in the safety analysis set, will include:

- Age (years at study baseline)
- Sex
- Race
- Ethnicity
- Weight (kg)

- Height (cm)
- Baseline peak work
- Baseline resting heart rate during the submaximal exercise test
- Baseline serum creatine kinase (CK)

Due to the number of measures, baseline characteristics will be provided in a separate summary. Continuous statistics will be provided for:

Reata Pharmaceuticals, Inc.

- Age at mitochondrial myopathy onset
- Years since mitochondrial myopathy onset (at study baseline)

Frequency tables (number and percentage) will be provided for discrete measures:

- Clinical diagnosis
- Stroke-like episodes in the past year
- Ophthalmoplegia in the past year
- Polyneuropathy in the past year
- Seizures in the past year

Demographic and baseline characteristics will be summarized by randomized treatment group.

#### 4.4 Medical History

Medical history will be mapped to preferred terms (PT) and system organ classes (SOC) using the Medical Dictionary for Regulatory Activities (MedDRA®) Dictionary (version 14.1). Medical history items will be summarized by MedDRA SOC and PT and patient listing will be provided.

#### 5. STUDY DRUG AND OTHER MEDICATIONS

#### 5.1 Prior and Concomitant Medications

Prior and concomitant medications will be coded using the World Health Organization (WHO) drug dictionary (B2\_DDE\_HD\_Sep2011-With PerfTerm) for anatomical therapeutic chemical classification (ATC) and preferred drug name.

A prior medication is any medication that is taken prior to the first dose of study drug. A concomitant medication is any medication taken at the time of first study treatment or a medication that was started after the start of study drug dosing. Specifically, concomitant medications are medications

- that are continued from screening and continued after the first study drug dosing, or
- that have start dates or stop dates within the treatment period.

A medication can be classified as both prior and concomitant if it was started prior to study treatment and continued during the treatment period.

Prior and concomitant medications will be summarized for each treatment group by WHO DD ATC class and preferred name. These summaries will present the number and percentage of patients using each medication. Patients may have more than one medication per ATC class and preferred name. At each level of patient summarization, a patient is counted once if he/she reported one or more medications at that level. Each summary will be ordered by descending order of incidence of ATC class and preferred name within each ATC class.

In addition, patients who take excluded medications sensitive substrates for cytochrome P450 2C8 or 3A4, moderate or strong inhibitors or inducers of cytochrome P450 3A4, or substrates for p-glycoprotein transporter (defined in the Protocol Section 9.2.1) during the study will be listed.

## 5.2 Duration of Study Treatment and Exposure to Study Drug

The duration of study drug exposure is defined as the number of days on treatment from the first dose of study drug until the last dose of study drug (last dose – first dose + 1). Study drug exposure will be summarized by descriptive statistics. Summaries will include the number of doses received (or dispensed), total dose (mg) received (or dispensed), average daily dose (mg), study drug compliance, and duration (days) of exposure during the study treatment period.

Total number of doses dispensed and total dose (mg) dispensed will be calculated from total number of kits (bottles) recorded on the Study Drug Dispensation eCRF. Total number of doses received will be calculated from information on the eCRF of Study Drug Return and Study Drug Dispensation, as the total number of doses dispensed – total number of doses returned. The total dose (mg) received can be calculated in similar way. The average daily dose (mg) will be calculated as total dose (mg) / (total number of days of exposure).

Study drug compliance (%) will be calculated as 100 × total number of doses received / total number of doses expected. Patients are expected to dose daily, therefore 84 doses expected at Week 12.

All study drug dispense and accountability data will be listed in patient listing.

#### 6. EFFICACY ANALYSIS

Primary analysis of the efficacy data will be based on the full analysis set, which will include all patients enrolled in Part 1 of the study. Analyses will be performed for each RTA 408 dose level. Summary statistics for observed values, change from baseline, and percent change from baseline (including 95% CI and quartiles) will be presented by randomized treatment group.

## 6.1 Primary Efficacy Analysis

Peak work (w/kg) is calculated as the maximum workload (w) at each visit divided by baseline weight (kg) for each patient. Peak work should be rounded to the nearest 0.0001 digit. A mixed-model for repeated measures (MMRM) analysis will be used to analyze the primary efficacy variable. All scheduled peak work values collected through the Week 12 visit will contribute to the primary analysis. The primary efficacy variable, the change from baseline in peak work value, will be calculated for each post first dose time point through Week 12 visit (i.e., Weeks 4 and 12). Missing data for the Phase 2 portion will not be imputed for the primary analysis. The primary inference will be the test of LS mean at each time point. The primary endpoint is the mean change from baseline in peak work at Week 12.

Patients must complete the maximal exercise test for at least 4 minutes to be considered a valid test. Maximal exercise test trials which were 4 minutes or less in duration will not be used in the primary efficacy analysis.

#### 6.1.1 Statistical Hypothesis

For the primary efficacy endpoint, the null hypothesis is the Week 12 mean ( $[\mu \, o_{MAV}] - [\mu \, PBO]$ ) change from baseline in peak work = 0 w/kg. The alternative hypothesis is the Week 12 mean ( $[\mu \, o_{MAV}] - [\mu \, PBO]$ ) change from baseline in peak work  $\neq 0$  w/kg.

A positive change from baseline suggests an improvement.

#### 6.1.2 Statistical Model

The MMRM model will include change from baseline in peak work as the dependent variable, treatment group, protocol scheduled time point (analysis visit), and the interaction between treatment and time as fixed effects, patient as a random effect. Analysis visits 0, 4, and 12 will be used. Within-patient correlations will be modeled using an unstructured covariance structure. Time ordering is a repeated measure within patients. It is assumed that errors for different patients are independent with an unstructured covariance structure. The estimation method for the model will be restricted maximum likelihood (REML). The SAS pseudo-code is as follows:

```
proc Mixed data=efficacy method=reml;
  Class usubjid trt avisit;
  model resp=trt avisit trt*avisit /s;
  repeated avisit / subject=usubjid type=un rcorr;
  lsmeans trt*week / diff cl alpha=0.05;
run;
```

In the event the MMRM model with an unstructured covariance structure does not converge, the following covariance structures will be as substitution in the following order. Each subsequent covariance structure will be used only if all previous covariance structure(s) is (are) used and the model(s) did not converge.

 Toeplitz covariance structure (assuming measurements from samples taken closer together in time are more highly correlated than those from samples taken farther apart).

Version 1 Date: 03Mar2018

- First order of auto-regressive [AR(1)] covariance structure (assuming measurements from samples taken closer together in time are more highly correlated than those from samples taken farther apart).
- Compound symmetry covariance structure (assuming equal correlation for measurements from a patient, regardless of how far apart in time when they were taken).

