#### 3.3 Strata and Covariates

Randomization in Part 1 of this study is not stratified. Since sample size per dose level will be small, no covariates will be considered for the primary analysis of Part 1.

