## 6.1.3 Reporting Results

The least squares (LS) mean, standard error (SE) of the LS mean, and two-sided 95% confidence interval (CI) of the LS mean and p-value will be reported at each time point for (1) each dose level of RTA 408 and (2) the difference between each dose and placebo. For part 1 of the study, statistical testing will be performed at every time point that peak work is measured. The difference between RTA 408 and placebo in change from baseline in peak work at Week 12 test is the primary endpoint. The mean change from baseline in peak work at all other time points will be considered exploratory, so tests at these time points will be performed with no adjustments for multiple comparisons.

A plot of the LS mean differences with 95% CIs of change from baseline in eGFR value over time will be presented for selected doses.

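### SAP 6.1.2 puts visit 0 in a model for change from baseline; fitted literally, the unstructured covariance is singular and the Toeplitz fallback gives about 11% type I error at equal variances

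*SAP*

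**What the plan says.** SAP 6.1.2 makes change from baseline in peak work the dependent variable, with treatment, visit and their interaction as fixed effects, estimated by REML. It then says: "Analysis visits 0, 4, and 12 will be used. Within-patient correlations will be modeled using an unstructured covariance structure". SAP 3.7.2 fixes the meaning of visit 0: "Baseline will be defined as analysis visit 0". SAP 3.3 adds that "no covariates will be considered for the primary analysis of Part 1".

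SAP 6.1 says something different about the same response. The change "will be calculated for each post first dose time point through Week 12 visit (i.e., Weeks 4 and 12"). Protocol 11.1 agrees with SAP 6.1. Protocol 11.3 gives Weeks 4, 8 and 12 for the 6-minute walk test (6MWT), and protocol 11.2 gives Weeks 4 and 12 for the submaximal test.

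SAP 6.1.2 also sets a fallback: "In the event the MMRM model with an unstructured covariance structure does not converge", the order is Toeplitz, AR(1), compound symmetry. "Each subsequent covariance structure will be used only if all previous covariance structure(s) is (are) used and the model(s) did not converge".

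Visit 0 is listed again in SAP 6.2 (6MWT, which uses the same model) and in 6.3.3 and 6.3.4 (submaximal measures). No section says that visit 0 rows stay out of the fit.

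**The concern.** The primary Part 1 model can be programmed in two ways, and each can claim to follow the SAP. Under SAP 6.1 there are two response rows per patient, Weeks 4 and 12. Under SAP 6.1.2 there are three, and the first is identically zero.

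SAP 6.1.3 does not exclude the second reading: "For part 1 of the study, statistical testing will be performed at every time point that peak work is measured". Peak work is also measured at screening. The pseudo-code does not settle it either, because its line "lsmeans trt*week / diff cl alpha=0.05" uses a term that is in neither the CLASS nor the MODEL statement.

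The choice matters because of the fallback. Toeplitz, AR(1) and compound symmetry, in the forms named, each use a single variance for all visits. A visit with no variance pulls that common value down, and the Week 12 standard error goes down with it. This would affect the dose-versus-placebo p-values and 95% intervals for peak work and for 6MWT.

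**Working it through.** **Inputs from the documents.** Two-sided 5% level (SAP 6.1.2, 6.1.3). Cohorts of 6 active and 2 placebo, up to 8 cohorts (SAP 1.2), with placebo pooled (SAP 3.1). If each cohort forms its own dose group, that is 8 × 6 + 16 = 64 patients in 9 groups, so 64 − 9 = 55 residual df.

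**Assumed, because the documents give no change-score variances.** Ratio R of Week 12 to Week 4 variance, 0.5 to 1.5. Correlation between the two changes 0.3, 0.5 or 0.8. Complete data. Toeplitz in its usual one-variance form. For reference, protocol 14.1 assumes compound symmetry with correlation 0.20 for Part 2. If that held for raw peak work at baseline, Week 4 and Week 12, each change would have variance 2σ²(1 − ρ) and the two changes covariance σ²(1 − ρ). That gives R = 1 and correlation 0.5.

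**Step 1: the plan's own level.** With visits 4 and 12 only, unstructured covariance and complete data, the Week 12 contrast is a two-sample t statistic on 55 df, so its size is exactly 5.0%. Simulation (8,000 trials) gave 4.9%.

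**Step 2: add visit 0 under the unstructured model.** The residual matrix S is zero in the visit 0 row and column, with 1 and R on the rest of the diagonal. REML minimises log|Σ| + tr(Σ⁻¹S). With visit 0 variance v, the −2 log-likelihood contains 55·log(v). This is −253.3 at v = 10⁻², −506.6 at 10⁻⁴, −1013.1 at 10⁻⁸ and −1519.7 at 10⁻¹², so there is no minimum. If v is held at 10⁻², 10⁻⁶ or 10⁻¹⁰ with zero visit 0 covariances, the fitted Week 12 variance is 1.00 of the truth at R = 0.5, 1 and 1.5. A near-boundary fit of this kind does no harm.

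**Step 3: the fallback.** Compound symmetry can be done by hand. The common variance is (0 + 1 + R)/3, which at R = 1 is 0.667 of the true Week 12 variance. Toeplitz was fitted numerically with multiple starts. Then

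type I error = 2·P(T₅₀ > t₀.₉₇₅,₅₀ × √(fitted/true variance)).

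For R = 1 and correlation 0.5 the ratio is 0.658. Its square root is 0.811, so the standard error is about 19% too small. The effective cut-off is 2.009 × 0.811 = 1.629, and the error is 11.0%. Using 41 or 55 df changes the error by at most 0.1 point.

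| R | Fitted/true Week 12 variance at correlation 0.3 / 0.5 / 0.8 | Type I error, peak work, Toeplitz |
|---|---|---|
| 0.5 | 1.031 / 1.060 / 1.108 | 3.9–4.7% |
| 0.67 | 0.828 / 0.836 / 0.869 | 6.7–7.4% |
| 1 | 0.663 / 0.658 / 0.656 | 10.8–11.0% |
| 1.5 | 0.554 / 0.551 / 0.541 | 14.1–14.6% |

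The error passes from conservative to inflated at R of 0.52 to 0.56. If Toeplitz also failed, at R = 1 AR(1) gives 10.8–11.5% and compound symmetry 10.7%.

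**Step 4: 6MWT.** With Week 8 variance midway and a common correlation, the Toeplitz ratios at R = 1 are 0.743 / 0.729 / 0.703, giving 9.0–9.8%. The error is 3.5% at R = 0.5 and 12.0–13.3% at R = 1.5.

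**Step 5: simulation under the null, Toeplitz fit, 8,000 trials each.**

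| Design | R | Correlation | Visit 0 kept | Visits 4 and 12 only |
|---|---|---|---|---|
| 8 doses of 6, 16 placebo | 1 | 0.5 | 10.5% | 4.9% |
| 6 doses of 6, 12 placebo | 1 | 0.5 | 10.7% | 5.1% |
| 6 doses of 6, 12 placebo | 1 | 0.8 | 11.0% | 5.2% |
| 6 doses of 6, 12 placebo | 0.5 | 0.5 | 4.2% | 5.1% |
| 6 doses of 6, 12 placebo | 1.5 | 0.5 | 14.0% | 5.2% |

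A small patient-level REML check (320 correlated tests per setting) gave 10.6% with complete data and 10.3% with 10% missing at Week 12.

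**The case against.** The strongest reply is that SAP 6.1 already answers the question. It defines the change only at post-dose visits, so no visit 0 response exists. The visit list in 6.1.2 then means only that visit 0 supplies the value subtracted, and testing a change from baseline at baseline would make no sense. That reading is natural and the protocol supports it. But 6.1.2 places the list in the model paragraph itself, nothing there limits visit 0 to that role, and the same list recurs in three further sections.

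The 11% also needs a chain of events: visit 0 rows fitted, the unstructured fit declared non-converged, and Toeplitz applied with similar variances at Weeks 4 and 12. This stands. SAS was not run, so whether it would declare non-convergence is unknown. Even the direction of the error depends on a variance ratio that the documents do not give.

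Finally, the consequence is limited. Part 1 has no confirmatory test and no multiplicity adjustment, Part 2 has a separate plan, and no section makes these p-values a dose-selection rule. All of that is accepted. It limits what is at stake but does not reconcile the two sections.

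**Conclusion.** The concern holds and should be fixed. SAP 6.1 and 6.1.2 conflict on which visits enter the primary model, and the literal reading of 6.1.2 makes the specified unstructured covariance singular. Confidence is high in the conflict and in the conditional arithmetic; whether inflation would actually occur has not been shown.

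On the adverse branch, the Week 12 peak-work test has a type I error of about 11% against a nominal 5% at equal variances. It is slightly conservative at a variance ratio of 0.5 and reaches about 14–15% at 1.5. 6MWT follows the same pattern, at 9.0–9.8% for equal variances. With complete data the point estimates do not change. On the harmless readings there is no error at all. No size is claimed for the submaximal models.

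**What to change.** In SAP 6.1.2, replace the visit list with: *The repeated response levels are analysis visits 4 and 12; visit 0 is used only to compute change from baseline.* In 6.2, list 4, 8 and 12. In 6.3.3 and 6.3.4, list 4 and 12, because no submaximal test is scheduled at Week 8 (protocol 11.2; SAP Table 1).

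As tidying, remove the patient random effect from the 6.1.2 text, since the code has none, and change trt\*week to trt\*avisit in the LSMEANS line.

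The cost is one-line edits in four places plus the tidying, with no new data, visits or patients. Compared with the Toeplitz fallback at equal variances and 8 cohorts, the corrected Week 12 peak-work intervals are about 23% wider (1/0.811 = 1.23; mean width 1.91 against 1.56 Week 12 SDs). That is the width needed for 95% coverage.

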## 6.1.3 Reporting Results

The least squares (LS) mean, standard error (SE) of the LS mean, and two-sided 95% confidence interval (CI) of the LS mean and p-value will be reported at each time point for (1) each dose level of RTA 408 and (2) the difference between each dose and placebo. For part 1 of the study, statistical testing will be performed at every time point that peak work is measured. The difference between RTA 408 and placebo in change from baseline in peak work at Week 12 test is the primary endpoint. The mean change from baseline in peak work at all other time points will be considered exploratory, so tests at these time points will be performed with no adjustments for multiple comparisons.

A plot of the LS mean differences with 95% CIs of change from baseline in eGFR value over time will be presented for selected doses.

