## 2.3.1 Efficacy Endpoints

The primary efficacy endpoint is change in peak work. Peak work will be derived by dividing the maximum work load (watts) at each visit by the patient's baseline weight (kg). Peak work will be rounded to the 0.0001 digit.

The secondary efficacy endpoint is the change in 6-minute walk test (6MWT) distance.

Exploratory endpoints for this trial include:

- To evaluate the change in peak oxygen utilization during maximal exercise testing
- To evaluate the change in peak blood lactate and pyruvate, peak heart rate, and rating of perceived exertion during submaximal exercise testing
- To evaluate the change in Fatigue Severity Scale score
- To evaluate the change in SF-36® Health Survey Update (SF-36) score
- Parameters assessed from blood lactate and serum pyruvate during submaximal exercise testing

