#### 6.3 Exploratory Efficacy

Summary statistics and 95% confidence intervals for treatment differences in mean change from baseline, using the same MMRM model used for the primary and secondary endpoints, will be provided for all exploratory endpoints unless otherwise noted. P-values will be provided for descriptive purposes only.

For parameters having repeated measurements within an analysis visit during the maximal and submaximal exercise test, the MMRM code should incorporate the analysis visit and assessment time (during the exercise test) in the analysis:

```
Proc Mixed data=x order=data;
Class patno trt week;
model resp = trt*time*week /s;
Repeated time*week / sub = patno type = un;
```

```
lsmeans trt*time*week / diff cl alpha=0.05;
Run;
```

For blood lactate measurements during the submaximal exercise test, the repeated measures model will incorporate baseline resting blood lactate as a covariate:

```
Proc Mixed data=x order=data;
  Class patno trt week;
  model resp = trt*time*week baseline_resting_lactate /s;
  Repeated time*week / sub = patno type = un;
  lsmeans trt*time*week / diff cl alpha=0.05;
  Run:
```

As with the primary and secondary endpoints, exploratory endpoints will be analyzed using individual doses of RTA 408 versus placebo pooled. A separate model that does not pool the RTA 408 doses will be used to obtain pairwise differences for each dose level versus pooled placebo.

For parameters having repeated measurements within an analysis visit during the maximal and submaximal exercise test, the change from resting (delta) for parameters measured at resting and a certain timepoint during the maximal or submaximal exercise test will be reported as:

Delta = [Parameter at Y min] – [Parameter at resting]

In the maximal exercise test, laboratory measurements may be measured at resting, at the end of the maximal exercise test, 5 min after the end of the maximal exercise test, and 10 min after the end of the maximal exercise test.

In the submaximal exercise test, efficacy and laboratory measurements are recorded at resting, at 10 min, 20 min, and 30 min.

The change from baseline is defined for parameters measured at resting and a certain timepoint during the maximal of submaximal exercise test is defined as:

Change from Baseline in Delta= [Parameter at Y (At Visit X) - Parameter at resting(At Visit X)] - [Parameter at Y min (At Baseline) - Parameter at resting(At Baseline)]

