Analysis visits 0, 4, 8 and 12 will be used. The pairwise dose group comparisons with placebo will be estimated using the difference in adjusted means and 95% CI for the difference in changes from baseline to Week 12.

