# 11. APPENDICES

Appendix 1. List of Laboratory Tests

Appendix 2. Programming Specifications

# Appendix 1. List of Laboratory Tests

Blood samples will be collected throughout the study for hematology, chemistry, and urinalysis for clinical laboratory evaluation.

Test panels will include the following:

Hematology	Chemistry	Urinalysis
Hematocrit	Blood urea nitrogen (BUN)	Specific gravity
Hemoglobin	Creatinine	Ketones
HbA1C	Total bilirubin	pH
Red blood cell (RBC) count	Alanine aminotransferase (ALT)	Protein
White blood cell (WBC)	Aspartate aminotransferase (AST)	Blood Glucose
Neutrophils	Alkaline phosphatase (ALP)	Urobilinogen
Bands (if detected)	Ferritin	Bilirubin
Lymphocytes	Sodium	Dilliuoni
Monocytes	Potassium	
Basophils (if detected)	Calcium	
Eosinophils (if detected)	Inorganic phosphorus	
Absolute platelet count	Magnesium	
Mean corpuscular	Chloride	
hemoglobin (MCH)	Bicarbonate	
Mean corpuscular volume	Uric acid	
(MCV)	Cholesterol	
Mean corpuscular hemoglobin concentration	Total protein	
(MCHC)	Glucose	
Reticulocyte count	Triglycerides	
	Albumin	
	Creatine phosphokinase (CPK)	
	Lactate dehydrogenase (LDH)	
	High-density lipoprotein cholesterol (HDL-C)	
	Low-density lipoprotein cholesterol (LDL-C)	
	Very-low-density lipoprotein cholesterol (VLDL-C)	
	Gamma-glutamyl transpeptidase (GGT)	
	Estimated glomerular filtration rate (eGFR) using the MDRD-4 formula	

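### SAP 6.1 to 6.3 (Part 1) contain six specification errors to correct before database lock; listing visit 0 in the change-from-baseline model is the one that could alter the primary result

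*SAP*

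**What the plan says.** SAP 2.3.1 names the endpoint: "The primary efficacy endpoint is change in peak work". SAP 6.1.3 sets out how that analysis is reported and ends with one figure of LS mean differences, in which "change from baseline in eGFR value over time will be presented for selected doses". Elsewhere in the visible SAP the quantity appears only in the chemistry panel of Appendix 1, as "Estimated glomerular filtration rate (eGFR) using the MDRD-4 formula".

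SAP 6.1.2 describes the model in prose as having treatment, visit and "the interaction between treatment and time as fixed effects, patient as a random effect", with an unstructured within-patient covariance. It lists analysis visits 0, 4 and 12, with change from baseline as the response. The printed code has a REPEATED statement with type=un and no RANDOM statement. It names the visit variable avisit in CLASS and MODEL, then requests "lsmeans trt*week / diff cl alpha=0.05". If the unstructured fit does not converge, the SAP moves in order to Toeplitz, AR(1) and compound symmetry.

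Both programs in SAP 6.3 declare "Class patno trt week" and then use time*week in REPEATED and trt*time*week in LSMEANS. For submaximal heart rate and lactate, SAP 6.3.3 and 6.3.4 say "Analysis visits 0, 4, 8 and 12 will be used". SAP Table 1 and Protocol 11.2 place the submaximal test at baseline, Week 4 and Week 12 only.

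**The concern.** An analysis plan fixes the output and the model before unblinding. Followed to the letter, this one draws the wrong variable in the figure for the primary endpoint, describes a covariance model with no unique solution, and supplies three programs that do not run. Someone then has to decide how to repair each item, and the decision should be on paper before the Part 1 lock.

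Most of the repairs are obvious and harmless. The visit 0 item is different, because the SAP itself says what happens when the unstructured model fails: it falls back to structures that assume one variance at all visits. A visit with no variance at all would pull that common variance down and understate the standard error at Week 12, which is the endpoint.

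**Working it through.** There is no stated figure to reproduce, so the check compares the sections with one another, counts parameters and then sizes the visit 0 effect.

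**1. Figure.** SAP 6.1.3 asks for LS mean differences in eGFR. SAP 7.2 gives chemistry results descriptive statistics only, so no visible model yields an eGFR LS mean. The peak-work model has no planned figure.

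**2. Random effect.** Let the marginal covariance be V = s²J + R, with s² the patient variance, J a matrix of ones and R unstructured. Adding any constant c to s² and subtracting it from every element of R leaves V unchanged.
- Two visits: 3 + 1 = 4 parameters, rank 3.
- Three visits: 6 + 1 = 7 parameters, rank 6.

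The patient variance is therefore not identifiable. V itself is the same with or without it, so the term is redundant.

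**3. Visit 0.** Change from baseline at baseline is zero for every patient. The 3×3 covariance of the responses at visits 0, 4 and 12 has a row and column of zeros: rank 2, determinant 0. REML has no proper unstructured solution, whether or not the random effect is coded.

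Now fit compound symmetry to those three visits with complete data. The common variance is the average of the diagonal. Let σ be the Week 12 SD of change and r the Week 4 SD divided by the Week 12 SD:
- pooled variance = (0 + r²σ² + σ²)/3 = σ²(r² + 1)/3
- Week 12 SE ratio k = √((r² + 1)/3)
- true two-sided error = 2·P(T > k·t₀.₉₇₅), on 55 df. This takes 64 patients (SAP 1.2) less 9 groups, assuming eight distinct doses plus pooled placebo and no dropout. The SAP states no df method.

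| r (assumed) | Pooled variance / σ² | SE ratio k | Two-sided error |
|---|---|---|---|
| 0.75 | 0.521 | 0.722 | 15.4% |
| 1.00 | 0.667 | 0.816 | 10.7% |
| 1.25 | 0.854 | 0.924 | 6.9% |

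At r = 1, large-sample fits of Toeplitz and AR(1), with an assumed Week 4 to Week 12 correlation of 0.2 to 0.7, give SE ratios of 0.80 to 0.82 and errors of 10.8% to 11.3%. The position in the fallback order therefore matters little. With Weeks 4 and 12 alone as responses, the unstructured matrix has 3 parameters and rank 3.

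**4. LSMEANS.** WEEK is in neither CLASS nor MODEL in the 6.1.2 program. The statement that should deliver the Week 12 contrast does not execute.

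**5. TIME.** PROC MIXED takes only classification variables in the REPEATED and LSMEANS effects, so neither 6.3 program runs as printed.

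**6. Week 8.** The submaximal row of SAP Table 1 has marks at Visits 2, 6 and 11 (Day 1, Day 28, Day 84) and none at Visit 8. The list with visit 8 is right for the walk test in SAP 6.2. For three exercise times, Weeks 4 and 12 give 6 repeated levels and 21 covariance parameters. The four listed visits would give 12 levels and 78 parameters, if all had data.

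**The case against.** The best defence is that these are slips a competent programmer would notice. Items 4 and 5 stop the program, so they cannot change an estimate. The random effect is absent from the printed code. Week 8 would normally be empty, and the comparison specified there is at Week 12. SAP 6.1 says the change is calculated for Weeks 4 and 12, so visit 0 in 6.1.2 may be meant only as the source of the baseline. Part 1 has no multiplicity control, and the exploratory p-values are descriptive. All of this stands and limits the severity. It does not remove the need to edit, because 6.1.2 lists visit 0 among the visits used for a model of change, and SAP 1 makes the SAP govern over the protocol.

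Four stronger readings are tempting, and the documents do not support them.
- A reader might infer that the random effect biases the primary test or drives it to the fallback. If the fit succeeds, the marginal covariance is unchanged. Adding the same term to a fallback structure on two visits still asks for 3 parameters where 2 can be identified, so the fallback would not cure it.
- A reader might infer that TIME would be fitted as a straight line. The programs do not run without TIME in CLASS, and once it is there it is categorical in MODEL as well. SAP 6.3.2 to 6.3.4 also ask for the visit-by-time interaction.
- A reader might infer that plotting selected doses hides results. SAP 6.1.3 requires LS means, intervals and p-values for every dose.
- A reader might extend the point to Part 2. SAP 2 puts that analysis in a separate document.

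**Conclusion.** All six items are in the current text and are wrong as written. Five have little or no effect on the numbers once repaired in the obvious way: the eGFR label, the redundant random effect, the LSMEANS term, the missing CLASS variable and the empty Week 8 level.

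The visit 0 item has a real size if it is followed literally. The Week 12 standard error is about 18% too small and the two-sided error is about 11%, assuming equal SDs at Weeks 4 and 12, complete data and use of a fallback structure. For SD ratios of 0.75 to 1.25 the error runs from about 15% down to about 7%. These ratios are assumptions; the documents give no SD of change by visit. If visit 0 serves only to compute the change, as SAP 6.1 suggests, the effect disappears.

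That eGFR has no model can be said only of the visible SAP, since its text passes from section 7.8 to section 10. Severity is minor to moderate: Part 1 is exploratory, although its results inform the choice of doses for Part 2.

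**What to change.** Make six edits to the SAP before the Part 1 database lock:

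1. 6.1.3: replace eGFR with peak work in the figure, and show every dose level.
2. 6.1.2, prose: delete the patient random effect, so that the text matches the code.
3. 6.1.2, visits: state that only Weeks 4 and 12 enter as responses and that visit 0 is used solely to compute the change. Apply the same wording where visit 0 is listed in 6.2, 6.3.3 and 6.3.4.
4. 6.1.2, code: request LS means of trt*avisit.
5. 6.3, both programs: add time to the CLASS statement.
6. 6.3.3 and 6.3.4: remove visit 8.

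The cost is a short SAP revision, with no new data, no protocol amendment and no change to the design.
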